APPENDIX C. QUALITY CONTROL AND QUALITY ASSURANCE

Protocol Amendments and Protocol Deviations

Protocol Amendments

No changes from the final approved (signed) protocol will be initiated without the prior written approval or favorable opinion of a written amendment by the Independent Ethics Committee/Institutional Review Board (IEC/IRB) and national and local competent authorities, as applicable, except when necessary to address immediate safety concerns to the patients or when the change involves only nonsubstantial logistics or administration. The principal investigator at each investigational center, the coordinating investigator (if applicable), and the sponsor will sign the protocol amendment.

Protocol Deviations

Any deviation from the protocol that affects, to a significant degree, (a) the safety, physical, or mental integrity of the patients in the study and/or (b) the scientific value of the study will be considered an important protocol deviation. Important protocol deviations may include non-adherence on the part of the patient, the investigator, or the sponsor to protocol-specific inclusion and exclusion criteria, primary objective variable criteria, or Good Clinical Practice (GCP) guidelines; noncompliance to investigational medicinal product administration; and use of prohibited medications. All protocol deviations will be reported to the responsible IEC/IRB, as required.

When an important protocol deviation is reported, the sponsor will determine whether to discontinue the patient from the study or permit the patient to continue in the study, with documented approval from the medical expert. The decision will be based on ensuring the safety of the patient and preserving the integrity of the study. A noncompliant patient may continue taking the study treatment only if this does not jeopardize the patient's safety. The sponsor will assess each protocol deviation and decide whether any of these noncompliances should be reported to the Regulatory Authority as a serious breach of Good Clinical Practice (GCP) and the protocol.

Changes in the inclusion and exclusion criteria of the protocol are **not** prospectively granted by the sponsor. If investigational center personnel learn that a patient who did not meet protocol inclusion and exclusion criteria was entered in a study, they must immediately inform the sponsor of the protocol deviation. A deviation from the eligibility criteria will always result in study drug discontinuation in case the patient has not been dosed. In case a patient who was wrongly enrolled has already started taking the study drug, a risk/benefit evaluation has to take place and a strong clinical justification must be provided in case the patient is not withdrawn from the study drug. If such patient has already completed the study or has withdrawn early, no action will be taken but the deviation will be recorded.

Information to Study Personnel

The investigator is responsible for giving information about the study to all personnel members involved in the study or in any element of patient management, both before starting the study and during the course of the study (eg, when new personnel become involved). The investigator must

ensure that all study personnel are qualified by education, experience, and training to perform their specific task. These study personnel members must be listed on the investigational center authorization form, which includes a clear description of each personnel member's responsibilities. This list must be updated throughout the study, as necessary.

The study monitor is responsible for explaining the protocol to all study personnel, including the investigator, and for ensuring they comply with the protocol.

Study Monitoring

To ensure compliance with GCP guidelines, the study monitor or representative is responsible for ensuring that patients have signed the informed consent form and the study is conducted according to applicable standard operating procedures (SOPs), the protocol, and other written instructions and regulatory guidelines.

The study monitor is the primary association between the sponsor and the investigator. The main responsibilities of the study monitor(s) are to visit the investigator before, during, and after the study to ensure adherence to the protocol; that all data are correctly and completely recorded and reported; and that informed consent is obtained and recorded for all patients before they participate in the study and when changes to the consent form are warranted, in accordance with IEC/IRB approvals.

The study monitor(s) will contact the investigator and visit the investigational center according to the monitoring plan. The study monitor will be permitted to review and verify the various records (case report forms [CRFs] and other pertinent source data records, including specific electronic source document relating to the study) to verify adherence to the protocol and to ensure the completeness, consistency, and accuracy of the data being recorded.

As part of the supervision of study progress, other sponsor personnel may, on request, accompany the study monitor on visits to the investigational center. The investigator and assisting personnel must agree to cooperate with the study monitor to resolve any problems, errors, or possible misunderstandings concerning the findings detected during the course of these monitoring visits or provided in follow-up written communication.

Audit and Inspection

The sponsor may audit the investigational center to evaluate study conduct and compliance with protocols, SOPs, GCP guidelines, and applicable regulatory requirements. The sponsor's Global Clinical Quality Assurance, independent of Global Specialty Development, is responsible for determining the need for (and timing of) an investigational center audit.

The investigator must accept that competent authorities and sponsor representatives may conduct inspections and audits to verify compliance with GCP guidelines.

APPENDIX D. ETHICS

Informed Consent

The investigator, or a qualified person designated by the investigator, should fully inform the patient of all pertinent aspects of the study, including the written information approved by the Independent Ethics Committee/Institutional Review Board (IEC/IRB). All written and oral information about the study will be provided in a language as nontechnical as practical to be understood by the patient. The patient should be given ample time and opportunity to inquire about details of the study and to decide whether or not to participate in the study. The above should be detailed in the source documents.

Written informed consent will be obtained from each patient before any study-specific procedures or assessments are done and after the aims, methods, anticipated benefits, and potential hazards are explained. The patient's willingness to participate in the study will be documented in the informed consent form (ICF), which will be signed and personally dated by the patient and by the person who conducted the informed consent discussion. The investigator will keep the original ICFs, and copies will be given to the patient. It will also be explained to the patient that a patient is free to refuse participation in the study and free to withdraw from the study at any time without prejudice to future treatment.

Competent Authorities and Independent Ethics Committees/Institutional Review Boards

Before this study starts, the protocol will be submitted to the national competent authority and to the respective IEC/IRB for review. As required, the study will not start at a given investigational center before the IEC/IRB and the competent authority (as applicable) for the investigational center give written approval or a favorable opinion.

Confidentiality Regarding Study Patients

The investigator must ensure that the privacy of the patients, including their identity and all personal medical information, will be maintained confidential at all times. In case report forms (CRFs) and other documents or image material submitted to the sponsor, patients will be identified not by their names, but by an identification number.

Personal medical information may be reviewed for the purpose of patient safety or for verifying data in the source and the CRF. This review may be conducted by the study monitor, properly authorized persons on behalf of the sponsor, Global Quality Assurance, or competent authorities. Personal medical information will always be treated as confidential.

Registration of the Clinical Study

In compliance with national and local regulations and in accordance with Teva standard procedures, this clinical study will be registered on trials registry websites.

APPENDIX E. WOMEN OF CHILDBEARING POTENTIAL AND BIRTH CONTROL METHODS

Assessment of likelihood of possible interaction between investigational medicinal products (IMPs) or concomitant medications and hormonal contraception should be conducted. Hormonal contraception may be susceptible to interaction with the IMP, which may reduce the efficacy of the contraception method.

Drug interaction studies have not been conducted with fremanezumab. Like other therapeutic antibodies, fremanezumab is expected to be primarily metabolized via proteolytic catabolism. Therefore, interaction with and impact on drug metabolizing enzymes (eg, cytochrome P450 [CYP] isoforms) is considered unlikely in humans.

In addition, fremanezumab is not expected to indirectly influence the CYP enzymes. In general, protein products that are cytokine modulators have been reported to affect the metabolism or disposition of co-administered medication by altering CYP enzymes/transporters (FDA 2012). Fremanezumab is an immunoglobulin G2 isotype, which is directed against a non-immunologic and soluble (not cell bound) target. Thus, the risk of cytokine release is considered to be low in the clinical setting. Furthermore, fremanezumab was tested for stimulation of proinflammatory cytokine release in human whole blood (Study 111320). Fremanezumab did not elicit significant cytokine release (TNF α , IL-6, INF γ , or IL-1 β) in any donor including at concentrations up to 100 $\mu\text{g/mL}$. As such, there is no reason to suspect that fremanezumab may influence CYP activity.

Women of non-childbearing potential are defined as:

- Surgically (hysterectomy, bilateral oophorectomy, or bilateral salpingectomy) or congenitally sterile
- One year postmenopausal (stable amenorrhea for 12 months without alternative medical cause plus high follicle-stimulating hormone (FSH) in the postmenopausal range) in women not using hormonal contraception or hormonal replacement therapy
- Women in stable post-menopause, but are taking hormone replacement therapy for the treatment of menopausal symptoms, may be considered eligible for the study even with the lower serum FSH. They do not need to use other contraception.

Highly effective birth control methods:

Highly effective birth control methods are methods that can achieve a failure rate of less than 1% per year when used consistently and correctly. Such methods include:

- Combined estrogen and progestogen hormonal contraception (oral, intravaginal, transdermal) associated with inhibition of ovulation; these should be initiated at least 7 days before dosing of IMP.
- Progestogen-only hormonal contraception (oral, injectable, implantable) associated with inhibition of ovulation; these should be initiated at least 7 days before dosing of IMP.

- Intrauterine device and intrauterine hormone-releasing system need to be in place at least 2 months before screening.
- Bilateral tubal occlusion
- Vasectomized partner provided that he is the sole sexual partner and has received medical assessment of the surgical process.
- Sexual abstinence is only considered a highly effective method if defined as refraining from heterosexual intercourse in the defined period. The reliability of sexual abstinence needs to be evaluated in relation to the duration of the clinical study and the preferred and usual lifestyle of the patient.
- Periodic abstinence (eg, calendar, ovulation, symptothermal, post-ovulation methods), declaration of abstinence for the duration of a study, and withdrawal are not acceptable methods of contraception (according to Medicines and Healthcare Products Regulatory Agency).

Acceptable birth control methods:

Acceptable birth control methods that result in a failure rate of more than 1% per year include: progestogen-only oral hormonal contraception for which the inhibition of ovulation is not the primary mode of action; male or female condom with or without spermicide; and cap, diaphragm, or sponge with spermicide. The combination of male condom with either cap, diaphragm, or sponge with spermicide (double barrier methods) are also considered acceptable but not highly effective methods of birth control.

Unacceptable birth control methods:

Periodic abstinence (calendar, symptothermal, postovulation methods), withdrawal (coitus interruptus), spermicides only, and lactational amenorrhea method are not acceptable methods of contraception. Female condom and male condom should not be used together.

Male contraception:

Male patients must always use a condom.

Vasectomy:

Use of contraceptive methods applies also to vasectomized men.

Pregnant female partners of male study participants:

Male study participants must use condoms during intercourse if their female partners are pregnant.

APPENDIX F. LOST TO FOLLOW-UP

A patient will be considered lost to follow-up if he/she repeatedly fails to return for scheduled visits and if the site is unable to establish contact with the patient after 3 documented attempts via 2 different methods (phone, text, e-mail, certified letter, etc).

The following actions must be taken if a patient fails to return to the investigational center for a required study visit:

- The investigational center must attempt to contact the patient and reschedule the missed visit as soon as possible, counsel the patient on the importance of maintaining the assigned visit schedule, and ascertain whether or not the patient wishes to and/or should continue in the study.
- In cases in which the patient is deemed lost to follow-up, the investigator or designee must make every effort to regain contact with the patient (where possible, 3 telephone calls and, if necessary, a certified letter to the patient's last known mailing address or local equivalent methods). These contact attempts should be documented in the patient's medical record.
- Should the patient continue to be unreachable, he/she will be considered to have withdrawn from the study with a primary reason of 'lost to follow-up'.

APPENDIX G. HANDLING, LABELING, STORAGE, AND ACCOUNTABILITY FOR INVESTIGATIONAL MEDICINAL PRODUCT(S)

Preparation of Investigational Medicinal Products

Fremanezumab and placebo will be provided in prefilled syringes contained in uniquely numbered kits and stored (refrigerated at 2°C to 8°C) at the investigational center. At the time of each study visit, the interactive response technology will be queried, and site personnel will retrieve the appropriately numbered kit(s). Kit numbers will be entered into the case report form.

Preparation instructions for subcutaneous (sc) injections: [REDACTED]

[REDACTED] A 1.5 mL volume from each syringe in each visit's kit(s) must be injected sc for dosing to be considered complete. Refer to [Appendix U](#) for additional details regarding recommended sc injection sites.

Storage and Security

The investigator or designee must confirm appropriate temperature conditions have been maintained for all IMPs received and any discrepancies are reported and resolved before use of the IMPs.

The test IMP (fremanezumab) and placebo IMP must be stored refrigerated at 2°C to 8°C (36°F to 46°F) and protected from light; the investigational center should have a process for monitoring the IMP storage temperature.

Diversion is considered to have occurred when the legal supply chain of prescription medicinal products is broken, and medicinal products are transferred from a licit to an illicit channel of distribution or use.

Labeling

Supplies of IMPs will be labeled in accordance with the current International Council for Harmonisation (ICH) guidelines on Good Clinical Practice (GCP) and Good Manufacturing Practice and will include any locally required statements. If necessary, labels will be translated into the local language.

Accountability

Each IMP shipment will include a packing slip listing the contents of the shipment, return instructions, and any applicable forms.

The investigator is responsible for ensuring that deliveries of IMPs and other study materials from the sponsor are correctly received, recorded, handled, and stored safely and properly in accordance with the Code of Federal Regulations or national and local regulations, and used in accordance with this protocol.

Only patients enrolled in the study may receive IMPs and only authorized staff at the investigational center may supply or administer IMPs. All IMPs must be stored in a secure, environmentally-controlled, and monitored (manual or automated) area in accordance with the

labeled storage conditions or appropriate instructions with access limited to the investigator and authorized staff at the investigational center.

The investigator, institution, or the head of the medical institution (where applicable) is responsible for IMP accountability, reconciliation, and record maintenance (ie, receipt, reconciliation, and final disposition records).

A record of IMP accountability (ie, IMP and other study materials received, used, retained, returned, or destroyed) must be prepared and signed by the principal investigator or designee, with an account given for any discrepancies. Empty and partially used prefilled syringes should be destroyed, and the investigational center should provide a certificate of destruction. If the investigational center does not have the capability to destroy the used and partially used prefilled syringes, the prefilled syringes should be sent back to the sponsor. Unused prefilled syringes of the IMP will be returned to the sponsor or designee.

APPENDIX H. PREVENTIVE CLUSTER HEADACHE MEDICATIONS AND DISALLOWED MEDICATIONS

Disallowed Medications Commonly Prescribed for Cluster Headache

The following medications will be considered as being used for the prevention of cluster headache attacks regardless of the initial indication:

- verapamil
- lithium
- methysergide
- valproate
- topiramate

Patients must start tapering these preventive medications as soon as they begin this study. The period of time needed to taper off these medications will be based on the investigator's medical judgment but should not exceed 1 month from the beginning of participation in this study.

Disallowed Concomitant Medications

Systemic steroids are not allowed during the double-blind treatment period of this long-term extension study.

Note that the only allowed steroids are intra-articular injection or ocular, ear drops, intranasal, inhaled, and creams for topical use.

APPENDIX I. ICHD-3 BETA DIAGNOSTIC CRITERIA

Refer to the International Classification of Headache Disorders, third edition (ICHD-3 beta) Diagnostic Criteria ([Headache Classification Committee of the International Headache Society 2013](#)) for additional details.

3.1 Cluster headache

Diagnostic criteria:

- A) at least 5 attacks fulfilling criteria B-D
- B) severe or very severe unilateral orbital, supraorbital and/or temporal pain lasting 15 to 180 minutes (when untreated)¹
- C) either or both of the following:
 - 1) at least 1 of the following symptoms signs, ipsilateral to the headache:
 - a) conjunctival injection and/or lacrimation
 - b) nasal congestion and/or rhinorrhea
 - c) eyelid edema
 - d) forehead and facial sweating
 - e) forehead and facial flushing
 - f) sensation of fullness in the ear
 - g) miosis and/or ptosis
 - 2) a sense of restlessness or agitation
- D) attacks have a frequency of between 1 every other day and 8 per day for more than half of the time when the disorder is active
- E) not better accounted for by another ICHD-3 beta diagnosis

3.1.1 Episodic cluster headache

Diagnostic criteria:

- A) attacks fulfilling criteria for 3.1 Cluster headache and occurring in bouts (cluster period)
- B) at least 2 cluster periods lasting from 7 days to 1 year (when untreated) and separated by pain-free remission periods of ≥ 1 month

3.1.2 Chronic cluster headache

Diagnostic criteria:

- A) Attacks fulfilling criteria for 3.1 Cluster headache and criterion B

¹ During part (but less than half) of the time course of 3.1 Cluster headache, attacks may be less severe and/or of shorter or longer duration

B) Occurring without a remission period or with remissions lasting <1 month, for ≥ 1 year

APPENDIX J. GUIDANCE ON SAFETY MONITORING

Guidance on Monitoring Patients with Elevated Liver Function Tests

Liver enzymes (alanine aminotransferase [ALT], aspartate aminotransferase [AST], gamma-glutamyl transpeptidase [GGT], and alkaline phosphatase [ALP]) as well as total, direct, and indirect bilirubin will be measured at each study visit.

In any case of elevated ALT or AST to a level exceeding $\geq 2 \times$ the upper limit of the normal range (ULN) (including patients whose baseline ALT or AST levels are $\geq 2 \times$ and $\leq 3 \times$ the ULN, who may be enrolled in the study), a thorough medical history and physical examination with a focus on liver disease should be undertaken.² In addition, the patient should be instructed to refrain from alcoholic beverages.

In case of symptoms compatible with drug-induced liver injury during the study, patients will be instructed to return to the investigational center for an unscheduled visit or to go to the emergency room to measure liver enzymes as soon as possible. Solitary elevations of total, direct, or indirect bilirubin, not accompanied by elevations of ALT or AST should be managed according to the discretion of the treating physician.

Elevation of Either ALT or AST to $\geq 3 \times$ ULN

Confirmation is required prior to IMP discontinuation in cases of elevation of either ALT or AST $\geq 3 \times$ ULN. (Note: In cases of elevation of ALT or AST $\geq 8 \times$ the ULN, no confirmation is required prior to IMP discontinuation, but the assessments below should be performed.) The following procedures should be followed:

- The day in which the abnormal value is received from the laboratory will be considered as day 0.
- The investigator should repeat the test for confirmation purposes (this may be performed in a local laboratory along with complete blood cell [CBC] count and differential to assess for eosinophilia; in general, in case a blood sample is sent to a local laboratory, the following assessments [and reference ranges] are mandatory: ALT [serum glutamic pyruvic transaminase], AST [serum glutamic oxaloacetic transaminase], ALP, bilirubin [total, direct, and indirect], CBC [with differential for eosinophil count, separate tube], and international normalized ratio (INR) [separate tube; not to be sent in a confirmatory test]). The investigator should also question the patient regarding symptoms.

The abnormality will be regarded as confirmed in each of the following scenarios:

- the baseline value was within the normal range and ALT or AST is still $\geq 3 \times$ the ULN

² Thorough medical history with a focus on liver disease: personal or family history of liver disease; personal history of a systemic disease with potential liver involvement; exposure to alcohol, medications (prescription or over-the-counter), herbal preparations, dietary supplements, recreational drugs, special diets, or environmental chemical agents; potential exposure to infectious agents (eg, travel to developing countries, history of potential exposure to blood or blood products, high-risk sexual relations); and any additional information deemed relevant by the investigator. Physical examination, including signs of chronic liver disease.

- the baseline value was above the ULN and ALT or AST is $\geq 2 \times$ the baseline value

Additional Tests/Evaluations:

Upon confirmation of the abnormality as noted above, the following additional evaluations should be performed and results should be recorded in the case report form:

- serology for hepatitis A (antibody and immunoglobulins M and G), B (core antibody total, core immunoglobulin M, and surface antigen), and C viruses (central laboratory)
- serology for autoimmune hepatitis: anti-nuclear antibodies (titer), anti-smooth muscle antibodies, and anti-liver kidney microsomal antibodies (central laboratory); further testing may be required in case of a positive result for hepatitis B or C
- ultrasound examination of the liver and biliary tract at the investigator's discretion
- other diagnostic tests/consultations as deemed necessary by the investigator (eg, serology for hepatitis E virus in case of travel to endemic geography)
- observation and follow-up (to be performed after the abnormality was confirmed as above)

ALT or AST $\geq 3 \times$ ($>3.5 \times$ the ULN if the Baseline Value is $>2.5 \times$ the ULN) but $<5 \times$ the ULN

In addition to the above procedures required for any elevation to levels $>3 \times$ the ULN:

- Alanine aminotransferase, AST, GGT, ALP, total bilirubin, direct bilirubin, indirect bilirubin, CBC and differential (to assess for eosinophilia), and INR should be monitored on days 5 (± 2 days), 8 (± 2 days), 14 (± 3 days), and 28 (± 3 days). On at least 1 of these days, the test should be performed centrally. (The INR should be sent to a local laboratory only.)
- In cases where a local laboratory is used, the results should be recorded in the CRF, accompanied by the reference range of the relevant measurements.
- Should the abnormality ($\geq 3 \times$ the ULN in case baseline was within the normal range or $\geq 2 \times$ the ULN in case the baseline value was above ULN but still $<5 \times$ the ULN) persist further, the patient will be followed according to the investigator's discretion, but a blood sample for ALT, AST, GGT, ALP, and total bilirubin, direct bilirubin, indirect bilirubin should be sent to the central laboratory at least once a month.

ALT or AST $\geq 5 \times$ but $<8 \times$ the ULN

In addition to the above procedures required for any elevation to levels $>3 \times$ the ULN:

- Alanine aminotransferase, AST, GGT, ALP, total bilirubin, direct bilirubin, indirect bilirubin, CBC and differential count (to assess for eosinophilia), and INR should be monitored twice a week.
- At least for every other measurement, the tests should be sent to the central laboratory. The rest of the tests may be sent to a local laboratory. The INR should always be sent to a local laboratory.

ALT or AST $\geq 8 \times$ the ULN

In addition to the above procedures required for any elevation to levels $>3 \times$ the ULN:

- The IMP should be discontinued immediately, and the early withdrawal visit should be performed.
- For follow-up guidance, please see below section “Follow-Up of Liver Enzymes after Stopping Rules Are Met.”

Stopping Rules

In the following circumstances, the IMP will be discontinued immediately:

- any increase in ALT or AST to $\geq 3 \times$ the ULN, combined with INR $>1.5 \times$ the ULN or total bilirubin $>2 \times$ the ULN
- any increase in ALT or AST to $\geq 3 \times$ the ULN, which is accompanied by symptoms clearly associated with impaired liver function (eg, vomiting, nausea, fever, rash, and eosinophilia) and not deemed related to other diseases (eg, vomiting or nausea triggered by cluster headache)
- any increase in ALT or AST to levels ≥ 5 but $<8 \times$ the ULN, which is persistent for ≥ 2 weeks of repeated measurements
- any increase in ALT or AST to levels $\geq 8 \times$ the ULN
- in any case where monitoring of liver enzymes cannot be performed according to the protocol guidance

Follow-Up of Liver Enzymes after Stopping Rules Are Met

- A patient who meets the above criteria for discontinuation of the IMP should be invited to the investigational center to return the IMP. Early withdrawal visit activities should be performed as soon as possible.
- Liver enzymes should be monitored until normalization or stabilization of the abnormality, according to the discretion of the investigator.
- In any case, following the early withdrawal visit, the minimal follow-up period will be 30 days and will include measurement of liver enzymes at least once weekly (may be performed in local laboratory, with at least 1 test being sent to the central laboratory).
- Every effort should be made to complete the additional tests/evaluations, as described above.

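### Appendix J asks for a repeat test before study drug is stopped, yet also orders an immediate stop, when ALT or AST is 3 to <8 x ULN with raised INR, raised bilirubin or liver symptoms

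*Protocol*

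**What the plan says.** All of the relevant text is in Protocol Appendix J (Guidance on Safety Monitoring).

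- **Confirmation.** Under the heading for ALT or AST at or above 3 x ULN: "Confirmation is required prior to IMP discontinuation in cases of elevation of either ALT or AST" at that level. A note gives one exception, for values of 8 x ULN or more, where "no confirmation is required prior to IMP discontinuation, but the assessments below should be performed".
- **What the repeat covers.** If it goes to a local laboratory, ALT, AST, ALP, bilirubin and a blood count with eosinophils are mandatory. INR is listed too, but marked "not to be sent in a confirmatory test". The investigator also asks about symptoms.
- **What counts as confirmed.** Either "the baseline value was within the normal range and ALT or AST is still" at least 3 x ULN, or "the baseline value was above the ULN and ALT or AST is" at least twice the baseline value. Only ALT or AST is considered.
- **Stopping Rules.** "In the following circumstances, the IMP will be discontinued immediately", followed by five rules. The first is any rise to 3 x ULN or more together with INR >1.5 x ULN or total bilirubin >2 x ULN. The second is any rise to 3 x ULN or more "which is accompanied by symptoms clearly associated with impaired liver function" and not put down to another disease. The third, for 5 to <8 x ULN, requires persistence over at least two "weeks of repeated measurements". The fourth is 8 x ULN or more. The fifth applies when liver enzymes cannot be monitored as the protocol directs.

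Protocol Sections 3.4 and 4.3 only refer the reader to Appendix J for these criteria. Neither ranks one instruction above the other.

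**The concern.** A site holding a result of, say, 4 x ULN with raised bilirubin is told in one place to confirm before stopping and in another to stop at once. Whichever it does, it departs from the protocol. This is also where clarity matters most. ALT or AST of at least 3 x ULN with bilirubin of at least 2 x ULN is part of the Hy's law definition in Section 7.1.5.1, and Section 1.3.1 names liver enzyme elevation as a potential risk. There is no Data Monitoring Committee (Section 5.9.3), so the site-level rules carry the weight. An injection cannot be taken back: Section 1.2.2.1 gives a mean half-life of 32.2 to 36.2 days. What is at stake is whether one more dose is given, or a required stop delayed, because the two texts disagree.

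**Working it through.** No design figure is involved. The check sets the two instructions side by side, then looks at whether they can lead to different actions and how much time is in play.

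**Step 1. Compare by enzyme band.**

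| ALT or AST (x ULN) | Other condition | Confirmation text | Stopping Rules | Result |
|---|---|---|---|---|
| ≥8 | none needed | waived | stop at once | agree |
| 5 to <8 | persists ≥2 weeks | confirm first | stop, on repeated values | no conflict |
| 3 to <8 | INR >1.5 x ULN or total bilirubin >2 x ULN | confirm first | stop at once | **conflict** |
| 3 to <8 | liver symptoms | confirm first | stop at once | **conflict** |
| 3 to <5 | none | confirm first | no rule | no conflict |

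The fifth stopping rule is not tied to an enzyme level. So 2 of 5 rules are affected.

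**Step 2. Can the two instructions lead to different actions?** The confirmation threshold is 3.0 x ULN for a normal baseline and 2 x baseline for a raised one:

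- baseline 1.1 x ULN: 2 × 1.1 = 2.2 x ULN
- baseline 1.2 x ULN: 2 × 1.2 = 2.4 x ULN
- baseline 1.5 x ULN: 2 × 1.5 = 3.0 x ULN, equal to the stopping-rule level

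Take assumed values: first ALT 3.4 x ULN, total bilirubin 2.3 x ULN, repeat ALT 2.9 x ULN.

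- First sample: 3.4 ≥ 3 and 2.3 > 2, so the first stopping rule is met.
- Repeat, normal baseline: 2.9 < 3.0, so not confirmed.
- Repeat, baseline 1.2 x ULN: 2.9 ≥ 2.4, so confirmed.

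In the normal-baseline patient the Stopping Rules end treatment, while the confirmation text does not yet allow it. Only for baselines above 1.5 x ULN does the confirmation threshold exceed 3 x ULN. Exclusion criterion d in Section 4.2 should make those uncommon, and the point does not rest on them.

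**Step 3. How much time is there before the next dose?** Scheduled laboratory tests are at visits 4, 7, 10 and 11 (Protocol Table 4; SAP Section 8.8). Visits are 28 days apart, each with a window of ±3 days.

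- After visit 4 or 7, next dosing visit: 28 − 3 − 3 = 22 to 28 + 3 + 3 = 34 days.
- Quarterly episodic group, next active dose: visits 5, 6, 8 and 9 are placebo (Section 5.1.1.1), so about 12 weeks; 84 − 3 − 3 = 78 to 84 + 3 + 3 = 90 days.
- After visit 10 or 11: no further dose. For visit 10 this assumes that the central result arrives after that day's injection.

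Appendix J also says that liver enzymes are measured at every visit, which does not match Table 4. If that were done, the next dosing visit would still be about four weeks off, though a sample at visit 3, 6 or 9 would precede an active quarterly dose by that interval.

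**The case against.** The best answer is that Appendix J runs in sequence: repeat, confirm, evaluate, monitor, stop. The 8 x ULN rule also sits under the instruction to stop immediately, yet the authors still wrote a separate waiver for it. That suggests that confirmation applies unless waived, so 3 to <8 x ULN would mean confirm, then stop at once. The repeat can support this, since bilirubin, eosinophils and symptoms are checked around it. INR is measured in the later follow-up, on days 5, 8, 14 and 28 or twice weekly depending on the level.

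This reading is arguable, but the text never states it, and it sits badly with stopping rules that apply to any increase and take effect at once. It also leaves a gap. Confirmation turns on ALT or AST alone, and the follow-up that includes INR starts only after confirmation. A patient who met a combination rule could therefore stay on drug because the repeat enzyme fell just short. The two-week rule having its own repeats does not settle the matter either way, because it is a persistence condition.

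The mitigating facts stand. Study personnel give the drug at the center (Section 5.1), so stopping means withholding a later injection. Section 4.3 lets the investigator withdraw a patient at any time (item 8) and requires it when an adverse event makes continuing contrary to the patient's interest (item 7). The fifth stopping rule would arguably catch a repeat that cannot be obtained.

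A reader might infer that patients with a potential Hy's law pattern will keep being dosed. The documents do not support that, given these safeguards and the intervals in Step 3.

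**Conclusion.** The point holds as a drafting conflict of low severity, limited to ALT or AST of 3 to <8 x ULN meeting either combination rule. It matters mainly when an unscheduled, symptom-driven sample, which Appendix J itself calls for, falls shortly before an active dose. Otherwise the repeat will usually be back before the next dosing visit.

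That the texts conflict rests on wording alone. The 3.4 and 2.9 x ULN example uses assumed values and shows only that the outcomes can differ. The documents give no basis for estimating how often this would happen.

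A reader might also suppose that the safety analysis or event reporting is compromised. It is not. Hy's law cases are reported as serious events under Section 7.1.5.1, and liver special-interest events under Section 7.1.7, without reference to this confirmation step. SAP Section 8.8 counts potentially clinically significant values from all postbaseline results.

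**What to change.** Extend the 8 x ULN note in Appendix J by one sentence: study drug may be stopped without a confirmatory result when ALT or AST is ≥8 x ULN, or is ≥3 x ULN and either combination rule under Stopping Rules is met, with the repeat test and other assessments carried out in parallel. Confirmation first then applies only to isolated elevations of 3 to <8 x ULN.

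Adding a condition of confirmation to the Stopping Rules would also remove the ambiguity. It is the weaker choice, because it leaves untreated by any rule the patient whose enzymes dip below the threshold on repeat while bilirubin, INR or symptoms remain a concern.

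The cost is the amendment text: no new tests, visits or patients, and no SAP change. The downside is that a few patients may be stopped, and taken through early-withdrawal procedures, on a value that a repeat would not have confirmed.
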